5.1.2.2 Treatment Materials Application

Following baseline sample collection, randomly assigned contralateral test areas will be treated with the applicable treatment materials. The post-application sampling times will be randomized among the sampling sites within a test area.

The treatment materials will be applied and the sampling configurations will be performed per the Randomization Scheme and the Study Material Treatment Application Instructions (Appendix 14.7). The duration of each application procedure will be recorded on the appropriate data capture form and transcribed in the eCRF.

The applicator weight (ZuraPrep™ or the pre-filled applicator for the reference control article or vehicle and empty applicator for the negative control) will be measured and documented before and after application to the treatment site. See Appendix 14.7 for details.

5.1.2.3 Timing of Post-Application Sample Collection

Microbial samples will be collected at 30 seconds (\pm 5 seconds) and 6 hours (\pm 30 minutes) post-treatment application for both the abdomen and the groin regions. Post-application timing begins upon completion of the treatment material application, including drying time. Microbial samples will be collected using the scrub cup technique (see Section 5.2.1).

Page 23 of 53 Zurex Pharma, Inc. Project: ZX-ZP-0092 Microbac Protocol: 865.1.03.25.18

Microbac Project: 865-107

After the 30 seconds (± 5 seconds) samples have been collected, sampling sites for 6 hours (± 30 minutes) will be covered indvidually with a piece of sterile gauze and a non-occlusive dressing to allow subjects restricted mobility and to protect the sites from contamination between sampling times. The subjects will be allowed to leave the clinical test facility, but must return at 6 hours (± 30 minutes) for the final post application sample collection

A skin irritation assessment will be performed prior to collection of the post-treatment microbial sample collection (30 seconds and 6 hours) and a corresponding rating score using the Skin Irritation Rating Scale for each individual skin condition will be recorded on the subject's data capture form and transcribed in the eCRF. See Appendix 14.11.

If an irritation score of 3 for any individual skin condition at any post-treatment observation is assigned, the subject will be discontinued from the study and an adverse event will be recorded. See Section 7.3 (Adverse Events). Following final sample collection, residual study materials will be wiped/cleansed from the subject's skin using mild soap and/or tap water with a paper towel.

5.2 Microbiological Methods

5.2.1 Microbial Sample Collection / Scrub Cup Technique

Quantitative cultures (screening baselines, treatment baselines and post-treatment application) will be obtained by a modification of the cylinder sampling technique of Williamson-Kligman scrub cup technique. To collect the samples, a sterile scrub cup will be placed on the site and held firmly to the skin. Sampling solution (SS) will be pipetted into the cup and the skin will be scrubbed in a circular motion with moderate pressure for 1 minute using a sterile rubber policeman. Using a sterile transfer pipette, the SS will be removed and placed in a sterile test tube. An additional of fresh sampling solution will be pipetted into the cup and the scrub procedure will be repeated. This solution will be pooled with the first solution collected.

5.2.2 Sampling Solution (SS)

The SS consists of sterile [75mM phosphate buffer	
- · · · · · · · · · · · · · · · · · · ·	ı
containing	
SS).	

5.2.3 Bacterial Enumeration Methods

Following sample collection, 10-fold serial dilutions will be prepared using Butterfield's Phosphate Buffered Water with

Page 24 of 53 Zurex Pharma, Inc. Project: ZX-ZP-0092 Microbac Protocol: 865.1.03.25.18

Microbac Project: 865-107

neutralizers (PBW). One mL aliquots of appropriate dilutions will be pourplated in triplicate using Trypticase Soy Agar containing neutralizers (TSA+N). Samples must be plated within 30 minutes of collection. After 72 \pm 4 hours of aerobic incubation at 30° \pm 2°C, colonies will be counted and viable cells in the original sample will be calculated according to Standard Operating Procedures. After incubation, plates may be refrigerated up to 48 hours prior to counting.

Raw colony counts from each dilution will be recorded on the appropriate data capture forms for each subject. The average number of microorganisms recovered (CFU/cm²) of skin for the screening and treatment day baseline samples will be calculated using the following formula to convert the plate CFU values into log₁₀ CFU/cm² of skin:

$$R = \log_{10} \left[\frac{F\left(\frac{\sum c_i}{n}\right)D}{A} \right]$$

Where:

R = the average CFU count in log_{10} scale per cm² of skin.

F = total mL of stripping fluid added to the sampling cylinder

 $\Sigma c/n$ = average of the triplicate colony counts for each sample collected

 $D = Dilution of the plates counted (10^0, 10^1, 10^2, 10^3, 10^4, or 10^5)$

A = Inside area of the sampling cylinder (

Dilution may be reported as dilution factor, which is the base 10 logarithm of the dilution. In that case, the factor of 'D' in the equation above will be replaced with 10^p.

5.2.4 Growth Promotion Control

For each batch of plating medium, TSA+N, fewer than 100 CFU of will be inoculated in a single plate pour plate. A 20-26 hours aged culture of will be serially diluted in dilution fluid. The CFU added will be confirmed using triplicate trypticase soy agar (TSA) spread plates. The plates will be incubated for 72 ± 4 hours of aerobic incubation at $30^{\circ} \pm 2^{\circ}$ C.

5.2.5 Neutralizer Validation

The effectiveness of the neutralizer system must be validated prior to the study start date to demonstrate that the antimicrobial is effectively neutralized and there is no effect on the growth of microorganisms. A procedure that will include in-vivo sampling will be combined with an in-vitro evaluation using procedures in accordance with ASTM E1054-08⁴ (2013). The procedure is Microbac - Confidential

Page 25 of 53 Zurex Pharma, Inc. Project: ZX-ZP-0092 Microbac Protocol: 865.1.03.25.18

Microbac Project: 865-107

attached as Appendix 14.10. These data must be provided in the final report.

5.3 Medication(s)/Treatment(s) Not Permitted

Topical or systemic antimicrobial exposure is not permitted within 14 days prior to the day of Screening Day, and during the study. Restrictions include, but are not limited to antimicrobial soaps, antiperspirants/deodorants, shampoos, lotions, perfumes, after shaves, colognes, and topical or systemic antibiotics. Exposure to antihistamines, immunosuppressants, or oral steroids within 14 days prior to Screening Day and up to and including Treatment Day (other than hormones for contraception or postmenopausal reasons) is not permitted.

5.4 Subject Compliance

Answers to the inclusion/exclusion questions (captured in the source documents and entered in the subject's eCRF) asked at the beginning of the screening and treatment phases will determine compliance to the Subject Instructions (Appendix 14.6) provided to each subject upon study participation. Documentation of the Inclusion/Exclusion criteria shall serve as confirmation of subject compliance with the Protocol.

6. Assessment of Efficacy

6.1 Efficacy Parameters

The primary measure of antimicrobial efficacy is the reduction of skin flora on the abdominal and groin sites 30 seconds following application of the study treatments relative to the Treatment Day baseline counts.

Product effectiveness will be measured using superiority and non-inferiority estimates for the 30-second sample time calculated using Average Treatment Effects (ATEs). The ATE will be estimated from a linear regression of the 30-second post-treatment bacterial count (log₁₀ scale) on the additive effect of a treatment indicator and the baseline or pre-treatment measurements (log₁₀ scale). To show effectiveness the test product will be 1) non-inferior to ChloraPrep® with a 0.5 margin (upper bound of 95% confidence interval of the ATE of the test product versus active control value < 0.5) and (2) superior to the ZuraPrep Vehicle (negative control) by a margin of 1.2 (lower bound of 95% confidence interval of the ATE of the test product versus the vehicle value > 1.2). Superiority and non-inferiority will be calculated separately for each body area (abdomen and groin).

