3.1 Study Type

This is a randomized, paired-comparisons design where each subject receives two of the planned treatments.

 Table 3.1:
 Treatments, Anatomical Sites of Evaluation, Application and Dry Times and Coverage

Areas (See Appendix 14.7 for detailed application instructions)

Treatment (Quantity/Volume)	Body Site	Application Time	Dry Time	Area of Coverage
ZuraPrep™	Abdomen (sebaceous poor)	30 seconds	3 minutes	5" x 5"
	Groin (sebaceous rich)	2 minutes	3 minutes	1.5" x 5"
ChloraPrep®	Abdomen (sebaceous poor)	30 seconds	3 minutes	5" x 5"
(active control)	Groin (sebaceous rich)	2 minutes	3 minutes	1.5" x 5"
ZuraPrep™ Vehicle,	Abdomen (sebaceous poor)	30seconds	3 minutes	5" x 5"
(negative control)	Groin (sebaceous rich)	2 minutes	3 minutes	1.5" x 5"

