3.2 Primary Endpoint/Analysis

The primary analysis for the study utilizes the standards of the Health Care Antiseptics, Topical Antimicrobial Drug Products Final Rule of December 20, 2017. The primary efficacy criteria will be assessed based on log₁₀ CFU/cm² values at 30 seconds for immediate effect and at 6 hours for persistent effect.

Product effectiveness will be measured using superiority and non-inferiority estimates for the 30-second sample time calculated using average treatment effects (ATEs). ATEs will be estimated from a linear regression of the 30 second post-treatment bacterial counts (log₁₀ scale) on the additive effect of a treatment indicator and the baseline or pre-treatment measurements (log₁₀ scale). To show effectiveness the test product will be (1) non-inferior to ChloraPrep® with a 0.5 margin (upper bound of 95% confidence interval of the ATE of the test product versus active control value < 0.5) and (2) superior to the ZuraPrep Vehicle (negative control) by a margin of 1.2 (lower bound of the 95% confidence interval of the ATE of the test product versus

Page 8 of 53 Zurex Pharma, Inc. Project: ZX-ZP-0092 Microbac Protocol: 865.1.03.25.18

Microbac Project: 865-107

the vehicle value > 1.2). Superiority and non-inferiority will be calculated separately for each body area (abdomen and groin).

A site is considered evaluable for efficacy (part of the per-protocol data set) if the criteria in the following table are met:

Table 3.2: Minimum and Maximum Treatment Day Baseline Values per Anatomical Site

Anatomical Site	Minimum and Maximum Treatment Day Baseline*
Abdomen	1.0 x 10 ³ – 3.2 x 10 ⁵ CFU/cm ² (3.0 Log ₁₀ – 5.5 Log ₁₀)
Groin	1.0 x 10 ⁵ - 3.2 x 10 ⁷ CFU/cm ² (5.0 Log ₁₀ - 7.5 Log ₁₀)

^{*}Note: For the Screening Day baseline, the maximum upper limit does not apply. Only the minimum criteria must be met.

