8.2 Statistical Methods

8.2.1 Efficacy Analyses

CFU values will be calculated as per the Bacterial Enumeration methods above. Individual plate CFU counts that are zero will be treated as 0.5 for further calculations.

Product effectiveness will be measured using superiority and non-inferiority estimates for the 30-second sample time calculated using average treatment effects (ATEs). ATEs will be estimated from a linear regression of the 30 second post-treatment bacterial counts (\log_{10} scale) on the additive effect of a treatment indicator and the baseline or pre-treatment measurements (\log_{10} scale). Superiority and non-inferiority will be estimated as follows:

Superiority and non-inferiority will be calculated separately for each body area.

Persistence or long-term efficacy is defined as having the 6 hours post-

Page 30 of 53 Zurex Pharma, Inc. Project: ZX-ZP-0092 Microbac Protocol: 865.1.03.25.18

Microbac Project: 865-107

treatment log₁₀ CFU/cm² values lower than or equal to the baseline log₁₀ CFU/cm² values for 100% of the subjects in each body area. Due to the normal variability associated with this biological system, the test article is considered to have persistent effect if the percentage of body sites with log₁₀ CFU/cm² values less than or equal to baseline for the 6-hour sample is between 95 to 100%. All subjects that do not achieve the 6-hour efficacy goal will be documented and discussed.

The efficacy calculations (superiority and persistence) only apply to ZuraPrep $^{\text{TM}}$ for the purpose of determining efficacy, but the same calculations will be performed for ChloraPrep $^{\text{R}}$ for information purposes only.

Summary statistics for the log₁₀ CFU/cm² values at each time point and the respective changes from baseline will be calculated, grouped by time point, test product, and body area. These statistics are for information purposes only and are not part of efficacy calculations.

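### Do the two primary decision rules in Sections 3.2 and 6.1 contradict each other because no subtraction order is given?

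*Combined protocol and SAP*

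**What the plan says.** The outcome model is in Section 6.1: "The ATE will be estimated from a linear regression of the 30-second post-treatment bacterial count", on the log10 scale, with a treatment indicator and the baseline measurement as additive terms. Sections 3.2 and 8.2.1 describe the same model. Fewer bacteria is the better result.

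Two criteria follow, applied separately to abdomen and groin:

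- Non-inferiority to ChloraPrep with a margin of 0.5: "upper bound of 95% confidence interval of the ATE of the test product versus active control value < 0.5".
- Superiority to vehicle. The purpose is stated as "superior to the ZuraPrep Vehicle (negative control) by a margin of 1.2" and the bound as "lower bound of 95% confidence interval of the ATE of the test product versus the vehicle value > 1.2". Section 3.2 uses nearly the same words: "lower bound of the 95% confidence interval of the ATE of the test product versus" the vehicle.

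Section 6.1 opens on the other scale: "The primary measure of antimicrobial efficacy is the reduction of skin flora". Section 8.3 likewise approximates the ATEs by mean reductions from baseline.

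Section 6.2 refers the reader to Section 8 for the analysis methods. There, Section 8.2.1 says "Superiority and non-inferiority will be estimated as follows" and ends in a colon. In the available copy, nothing follows before the next sentence.

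**The concern.** Both rules use the same form of words, the test product *versus* the comparator, yet one asks for a small upper limit and the other for a large lower limit. A reader who takes *versus* to mean *minus*, and codes the treatment indicator the same way both times, finds that one of the two rules cannot do its job.

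These are the pass/fail rules for the primary endpoint. A wrong sign against vehicle would fail an effective product. A wrong sign against ChloraPrep would let an inferior product pass and could fail a better one. The mixture of count and reduction language in Section 6.1 makes the slip easier to imagine.

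**Working it through.** **Scale.** Write Y for the 30-second log10 count, B for baseline and T for the treatment indicator, with Y = a + τT + βB. The reduction is B − Y = −a − τT + (1 − β)B. Its treatment coefficient is −τ, so with baseline in the model the count and reduction scales give the same estimate with opposite sign. The reduction language introduces a sign question and no second analysis.

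**Layout.** Section 3.1 states that "each subject receives two of the planned treatments". With 108 subjects and three treatments, 108 × 2 / 3 = 72 sites per treatment and body area, which reproduces Table 1.5. Equal pairing, assumed here, gives 108 / 3 = 36 subjects per treatment pair. The 65 per treatment in Section 8.3 cannot be reproduced because its assumed effects and SDs are not in the available text. The sign question does not depend on it.

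**The possible orders.** Assumed for illustration: mean reductions of 2.5 (test), 2.5 (ChloraPrep) and 0.8 (vehicle), SD 1.0, independent sites. SE = 1.0 × √(2/72) = 0.167 and 1.96 × SE = 0.33.

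| Order, on counts | Against ChloraPrep, upper limit < 0.5 | Against vehicle, lower limit > 1.2 |
|---|---|---|
| Test minus comparator for both | 0.00 (−0.33, 0.33): works | −1.70 (−2.03, −1.37): cannot pass |
| Comparator minus test for both | Inverted: a product 1.0 worse gives −1.00 (−1.33, −0.67) and passes; one 1.0 better gives 1.00 (0.67, 1.33) and fails | 1.70 (1.37, 2.03): works |
| Test minus ChloraPrep; vehicle minus test | Works | Works |

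**Size of a wrong sign.** Assumed: SD 0.8 to 1.2 and within-subject correlation ρ from 0 to 0.5. SE = SD × √((2/72)(1 − ρ/2)), which runs from 0.8 × √(0.0278 × 0.75) = 0.115 to 1.2 × √0.0278 = 0.200.

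- *True benefit over vehicle of 2 log10.* The test-minus-vehicle interval runs from (−2.23, −1.77) to (−2.39, −1.61), so a lower limit above 1.2 is effectively impossible. For vehicle minus test at the larger SE, (2 − 1.2)/0.200 − 1.96 = 2.04, giving probability 0.979; the range is 0.979 to 1.000.
- *True deficit to ChloraPrep of 0.5.* The pass probability is 0.025 in the intended direction and 0.999 to 1.000 in the reverse.
- *True deficit of 0.3.* In the intended direction, 0.2/0.200 − 1.96 = −0.96 and 0.2/0.115 − 1.96 ≈ −0.23, giving 0.17 to 0.41. In the reverse, the probability is 0.98 to 1.00.
- *Products equal.* Direction makes no difference: 0.71 to 0.99 either way.

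The printed model has no subject term. Without the pairing adjustment, the smallest SE is 0.8 × √(2/72) = 0.133 and the first interval becomes (−2.26, −1.74). The signs do not change.

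**Which order the text supports.** The table shows what follows *if* one order is imposed on both rules. The plan does not impose one, because *versus* names the two products and specifies no subtraction. The purpose of each rule settles the direction. Non-inferiority on counts means limiting how far the test count can exceed ChloraPrep's, so test minus ChloraPrep is bounded above by 0.5. Superiority by 1.2 means showing that the vehicle count exceeds the test count by more than 1.2, so vehicle minus test is bounded below by 1.2. Taken literally, test minus vehicle above 1.2 would require the product to leave over 1.2 log10 *more* bacteria than vehicle, which contradicts the word superior in the same sentence.

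**The case for a change.** The strongest argument for a change is that decision rules for a primary endpoint should not have to be inferred, and that stating the order costs one clause in each of two sections. A wrong sign against vehicle would be conspicuous, since an effective product would show a large negative interval. A wrong sign against ChloraPrep might not be: an analyst could orient the ATE so that superiority works, keep that orientation, and obtain a plausible small number. At a true deficit of 0.3 log10 that would move the pass probability from 0.17–0.41 to 0.98–1.00. Section 8.2.1 also repeats the superiority calculation for ChloraPrep, which adds a further contrast needing a direction.

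The algebra stands, and so does the observation that the visible wording leaves the sign unstated. What does not follow is that the plan directs anyone to the wrong contrast. On the specified count outcome, the customary test-minus-control order makes the ChloraPrep rule correct as printed. The false pass arises only if that order is reversed, or the scale switched, while the stated purpose is ignored. The ChloraPrep calculation is informational and takes the same direction, vehicle minus product. The probabilities describe the effect of a sign flip and say nothing about how likely one is.

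**Conclusion.** The concern does not hold as a defect in the primary analysis. Sections 3.2 and 6.1 leave a sign convention unstated, but the purpose beside each bound admits only one sensible direction: test minus ChloraPrep with the upper 95% limit below 0.5, and vehicle minus test with the lower 95% limit above 1.2. A competent analyst would use these, so writing them out would alter no estimate, margin, sample size or conclusion.

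This rests on the outcome being the post-treatment log10 count, which three sections state, and on the purposes in Sections 3.2 and 6.1 being read as written. It does not depend on the SDs, correlations or effects assumed above, which affect only the size of a hypothetical miscoding. Nor does it depend on the text after the colon in Section 8.2.1. That text may define the contrasts explicitly, and its absence from the available copy cannot be counted as an omission from the plan.

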6.1.1 Secondary Endpoints/Analysis

Persistence or long-term efficacy is defined in the Final Rule as having the 6 hours post-treatment log_{10} CFU/cm² values lower than or equal to the baseline log_{10} CFU/cm² values for 100 percent of the subjects in each indication and body area. Due to the normal variability associated with this biological system, the test article is considered to have persistent effect if the percentage of body sites with log_{10} CFU/cm² values less than or equal to

Page 26 of 53 Zurex Pharma, Inc. Project: ZX-ZP-0092 Microbac Protocol: 865.1.03.25.18

Microbac Project: 865-107

baseline for the 6-hour sample is between 95 to 100%. All subjects that do not achieve the 6-hour efficacy goal will be documented and discussed. This only applies to ZuraPrep™ for the purpose of determining efficacy, but the same calculation will be performed for ChloraPrep® for information purposes only.

6.1.2 Study Validity

There are no study validity criteria. All calculations performed for ZuraPrep™ will be performed for ChloraPrep® to the for informational purposes only.

6.2 Assessment Methods

Efficacy will be assessed by sampling the skin using the cup scrub method described in Section 5.2. See Section 8 for analysis methods.

7. Assessment of Safety

7.1 Safety Parameters

The principal measures of safety will be the recording of skin irritation scores and the incidence of adverse events reported during the study.

7.2 Assessment Methods for Skin Irritation

After the washout period, the Investigator or designated sub-investigators trained by the Investigator will assess the subject's skin condition and assign a skin irritation rating score using the Skin Irritation Rating Scale (see Appendix 14.11). A skin irritation score will be recorded at both the screening and treatment phases prior to baseline sample collections and prior to each post-treatment application sample collection (30 seconds, and 6 hours).

A corresponding rating score for each individual skin condition, for each site will be recorded on the appropriate data capture form and entered in the subject's eCRF. (See Appendix 14.11, which includes the following four independent evaluation categories: Erythema, Edema, Rash, and Dryness).

If an irritation score of 1 or greater for any individual skin condition prior to the baseline sample collection (at either the screening or treatment day phases) is assigned, the subject will be excluded from the study (no study treatment will be applied).

If an irritation score of 3 for any individual skin condition at any observation period is assigned, the subject will be discontinued from the study and an adverse event will be recorded. See Section 7.3 (Adverse Events).

7.3 Adverse Events

The Investigator is responsible for identifying adverse events that occur to each

Microbac - Confidential

Page 27 of 53 Zurex Pharma, Inc. Project: ZX-ZP-0092 Microbac Protocol: 865.1.03.25.18

Microbac Project: 865-107

subject throughout the study and follow-up period. An adverse event can occur at any time during the conduct of the study. Adverse events will be captured for all subjects from the time of screening baselines are taken until the time of discharge from the study. An adverse event can be identified by the Investigator or reported by the subject.

Note: The Federal Privacy Rule (HIPAA) specifically permits the use and disclosure of protected health information "without written authorization of the individual" when used for public health activities such as reporting adverse events, tracking FDA-related products, enabling recalls, repairs, replacements, lookbacks, or conducting post-market surveillance [45 CFR 164.512]. This use and disclosure is subject to the minimum necessary standard, i.e. "the minimum necessary to accomplish the intended use, disclosure, or request" [45 CFR 164.502(b)(1)].

Definitions:

Adverse Event/Experience

An Adverse Event/Experience is any unexpected or undesirable experience occurring to a subject during a study, which may or may not be related to the test article. All adverse event/experiences will be recorded and reported according to the Standard Operating Procedures of the laboratory.

All adverse events, regardless of severity or the causal/effect relationship, will be recorded. The severity of the effect will be noted as "Mild," "Moderate," or "Severe" according the following definitions:

Mild Awareness of signs or symptom, but easily tolerated.

Moderate Discomfort to a degree as to cause interference with normal daily

life activities and /or requiring medication.

Severe Incapacity with inability to work or do usual daily life activities and

requiring medical attention/intervention.

Causal Relations of Adverse Event/Experience

When determining the causal/effect relationship to the test article, the relationship will be described as "None," "Possible," "Probable," or "Definite." The following definitions will be utilized:

None No association to the test article. Related to other etiologies such as

concomitant medications or conditions or subject's known clinical

state.

Possible Uncertain association. Other etiologies are also possible.

Probable Clear-cut association with improvement upon withdrawal of the test

article. Not reasonably explained by the subject's known clinical state

Page 28 of 53 Zurex Pharma, Inc. Project: ZX-ZP-0092 Microbac Protocol: 865.1.03.25.18

Microbac Project: 865-107

Definite

An adverse event with a clear-cut temporal association with exposure to study materials and cannot reasonably be explained by the subject's known clinical state. Association with study material is confirmed by laboratory testing if possible.

Serious Adverse Event/Experience

A Serious Adverse Event/Experience is any adverse experience occurring at any dose that results in any of the following outcomes:

- Death;
- A life-threatening adverse drug experience;
- Inpatient hospitalization or prolongation of existing hospitalization;
- A persistent or significant disability/incapacity;
- Congenital anomaly/birth defect;
- An important medical event that may require medical or surgical intervention to prevent one of the previously listed outcomes.

Unexpected Adverse Event/Experience

An Unexpected Adverse Event/Experience is any adverse drug event/experience not listed in the current labeling for the test article or the current Investigator's brochure. Where test article labeling or Investigator's brochure is not available, anticipated experiences will be based on the known pharmacological/toxicological properties of the test article or ingredients.

Recording and Reporting

The Investigator or designee records all adverse events on an Adverse Event Record that will be transcribed in the subject's eCRF. Documentation includes the AE description, term, severity, seriousness, date of onset and resolution, relationship to the test article, action taken and outcome.

The Investigator must promptly report all treatment related adverse events to the Sponsor within two business days. All serious adverse events must be reported to the Sponsor and to the IRB within 24 hours of the Investigator awareness/notification of the event.

If a subject has no adverse event during the study, the absence of such must be recorded on the eCRF.

